14.1.1 Primary Objective: Objective Response Rate

Objective Response Rate (ORR)

The ORR is the proportion of participants having a confirmed Objective Response (OR) in the analysis set.

The confirmed objective response according to RECIST 1.1 as adjudicated by the IRC is the primary endpoint of the study. The study aims to estimate the Objective Response Rate (ORR) with a sufficient level of precision and that the associated lower bound of the two-sided 95% CI is above a minimal threshold of 15%.

Confirmed Objective Response (OR)

The Confirmed Objective Response (OR) is defined as a best overall response of confirmed complete response (CR) or partial response (PR) according to RECIST v1.1 as adjudicated by IRC.

Best overall response will be assessed based on reported overall responses at different evaluation time points from the treatment start date until documented disease progression in accordance to RECIST v1.1, taking requirements for confirmation into account as detailed below. Only tumor assessments performed before the start of any subsequent anti-cancer therapies will be considered in the assessment of best overall response. If a tumor assessment was performed on the same day as start of new anti-cancer therapy, it will be assumed that the tumor assessment was performed prior to the start of the new anti-cancer therapy, therefore the tumor assessment will be included in the assessment of best overall response. Clinical deterioration will not be considered as documented disease progression. The date of the overall response assessment is the earliest date for imaging of target, non-target and new lesions of images taken at that response assessment.

Best Overall Response based on confirmed responses according to RECIST 1.1 will be derived as follows

- CR = at least two determinations of CR at least 4 weeks apart (with no PD in between)
- PR = at least two determinations of PR or better (PR followed by PR or PR followed by CR) at least 4 weeks apart (and not qualifying for a CR), with no PD in between
- SD = at least one SD assessment (or better) \geq 6 weeks after first date of study intervention and before progression (and not qualifying for CR or PR) Non-CR/Non-PD = at least one Non-CR/Non-PD assessment \geq 6 weeks after first date of study intervention and before progression with no measurable disease and does not meet criteria of CR

Note: As tumor lesions are evaluated by the IRC, it may happen that the independent reviewer disagrees with the Investigator and does not assess any tumors as “measurable” at screening. However, as per inclusion criteria, measurable disease must be confirmed by IRC at inclusion, so such case is not expected to occur. But in case of Non-CR/Non-PD, the overall response is rated as “non-CR/non-PD” (if no “CR” or “PD” are previously reported) by the IRC. Non-CR/Non-PD is specific to IRC assessment (it does not apply to Investigator assessment)

- PD = progression \leq 16 weeks after first date of study intervention (and not qualifying for CR, PR, non-CR/non-PD or SD).
- Not Evaluable (NE): all other cases.

Disease Control Rate (DCR)

Disease Control Rate (DCR) is defined as the proportion of participants with best overall response according to evaluation criteria of confirmed CR, PR, or SD out of the total number of participants in the analysis set.

Best Overall Response based on unconfirmed responses

Best Overall Response can be assessed based on unconfirmed responses according to RECIST 1.1 and derived as follows:

- CR = at least one determination of CR

- PR = at least one determination of PR (and does not meet criteria of CR)
- SD = at least one SD assessment ≥ 6 weeks after first date of study intervention and before progression (and does not meet criteria of CR or PR)
- Non-CR/Non-PD= at least one Non-CR/Non-PD assessment ≥ 6 weeks after start date and before progression with no measurable disease (and does not meet criteria of CR)

Note: As tumor lesions are evaluated by the IRC, it may happen that the independent reviewer disagrees with the Investigator and does not assess any tumors as “measurable” at screening. However, as per inclusion criteria, measurable disease must be confirmed by IRC at inclusion, so such case is not expected to occur. But in case of Non-CR/Non-PD, the overall response is rated as “non-CR/non-PD” (if no “CR” or “PD” are previously reported) by the IRC. Non-CR/Non-PD is specific to IRC assessment (it does not apply to Investigator assessment)

- PD = progression ≤ 16 weeks after first date of study intervention (and does not meet criteria of CR, PR, SD)
- NE = all other cases.

Details of analyses

Separate tables will be provided for Best Overall Response based on confirmed and unconfirmed responses. Best Overall Response based on confirmed responses of CR, PR, SD, PD and NE as well as the ORR and the DCR will be provided with number and percentage of participants.

The number and percentage of participants will be provided for Best Overall Response of CR or PR based on unconfirmed responses within 8 weeks before the cutoff. The participants will be taken into account only if their first CR or PR occurred within 8 weeks before the cutoff, they don't have confirmed response of CR or PR and they continue to have tumor assessments (they didn't discontinue the study for any reason and didn't discontinue treatment because of progressive disease). The denominator will be all participants in the analysis set.

The ORR and DCR will be provided with a two-sided 95% CI using the Clopper-Pearson method (exact CI for a binomial proportion as computed by default by the FREQ procedure using the EXACT option).

For all participants, the individual percentage of change in the sum of diameter since baseline will be displayed over time on a spider plot, together with the first occurrence of new lesion and the participant off treatment. The change in the sum of diameters between baseline and the best post-baseline assessment (i.e. minimum change since baseline) for these participants will be displayed on a waterfall graph. The sum of diameters includes all target lesions (longest diameter for non-nodal lesions and short axis for nodal target lesions). Same spider plot will be performed only on participants with a response, confirmed, unconfirmed or delayed.

For spider plots and waterfall plots, the percent change from baseline in the sum of diameters will be displayed for valid timepoint assessments, only. For the purpose of this analysis, a valid timepoint assessment is defined as a complete assessment of all target lesions reported at baseline.

Further, split and coalesced lesions have to be taken into account appropriately to determine if a timepoint assessment is valid to derive the percent change from baseline in sum of diameters. All sum of diameters will be used, including the ones beyond first PD (for waterfall plot, the best post-baseline sum of diameters will be used even if occurring beyond PD). For waterfall plot, the percent change from baseline to 8-weeks assessment, as well as the percent change from baseline to the best post-baseline sum of diameters will be displayed for each participant.

The best percent change in sum of target lesion diameters will also be presented in a waterfall plot with confirmed Best Overall Response per IRC, histology, prior Bevacizumab use, prior anti-cancer radiotherapy, Moore criteria, number of prior treatment lines (0, 1 and ≥ 2) and PD-L1 expression at baseline measured by central lab (see section 8.2). A spider plot including all subjects with at least one target lesion previously irradiated will be provided. This plot will display the individual percentage of change in the sum of diameter since baseline for the target lesions previously irradiated and the curves will be color-coded to differentiate responder vs non-responder subjects.

Two listings of tumor assessment will be provided with the following information. First listing will display participant identifier, age, sex, race, first and last date of treatment, date of start of subsequent anticancer therapy, date of death when death occurs, visit, date(s) of imaging, description of target lesions (size, site, type, method), non-target lesions (status, site, type, method), and new lesions (site, type, method) and if the lesion split or merged. Second listing will present participant identifier, age, sex, race, first and last date of treatment, Best Overall Response based on confirmed responses, Best Overall Response based on unconfirmed responses, date of start of subsequent anticancer therapy, date of death when death occurs, target response, non-target response, new lesion, sum of diameters, % of change in sum of diameters since baseline and overall response.

In addition, a summary table of the reasons for non-evaluable Best Overall Response based on confirmed responses will be provided, the following reasons will be detailed:

- No baseline assessment (if applicable)
- No post-baseline assessments due to death within 8 weeks after the start of study treatment
- No post-baseline assessments due to other reasons
- All post-baseline assessments have overall response ‘Non-evaluable’
- New anticancer therapy started before first evaluable post-baseline assessment
- SD of insufficient duration (< 6 weeks after the start of study treatment)

Note: Special cases where Best Overall Response is NE due to both early SD and late PD will be classified into this category

- Non-CR/Non-PD of insufficient duration (<6 weeks after the start of study treatment) (if required by the data)
- No evaluable tumor assessment > 16 weeks followed by PD (i.e. tumor assessment of PD was > 16 weeks after start of study treatment and there was no evaluable tumor assessment in between)

- No IRC review and Not determined categories may also be added if applicable

A listing of reasons for non-evaluable Best Overall Response based on confirmed responses will also be created including: participant identifier, age, sex, race, date of first and last dose, date(s) of imaging, overall response and the reason for Best Overall Response based on confirmed responses non-evaluable.

Clinical efficacy of Bintrafusp alfa will be evaluated according to PD-L1 expression as a Secondary Endpoint, see section 16.5.1.

The following SAS code will be used to analyse the primary endpoint, ORR with its 95% CI:

```
proc freq data = <DATASET>;  
    table <VARIABLE> / binomial(exact) alpha=.05 out = <OUTDATASET>;  
run;
```

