7.1.2 Rechallenge

7.1.2.1 Reinitiation

One reinitiating course of treatment at the same dose and schedule and treatment duration up to 24 months is allowed at the discretion of the Investigator and agreement of the Medical Responsible for:

- Participants who are experiencing SD, a PR, or CR at the time of discontinuation, and then subsequently develop disease progression after stopping therapy, but prior to the End of the Study.

OR

- Participants who are discontinued due to an AE that is subsequently well managed or resolved after stopping therapy, but prior to the End of the Study.

The participant should reinitiate treatment at the treatment phase visit where they left off according to the SoA (see Table 1). Participants who reinitiate treatment should stay on study and should be treated and monitored according the SoA for the rest of the study.

Prior to reinitiation, the Investigator will need to confirm that the benefit of reinitiating treatment outweighs any risk involved, such as that which led to initial treatment discontinuation. For participants with only stable disease at the time of discontinuation, the Investigator should confirm that no other reasonable treatment options are available. In addition, to be eligible for reinitiation, the participant must not have previously withdrawn consent for this trial and should have been followed up with regular eCRF documented evaluation scans up to reinitiation of treatment.

A rebaseline scan must be performed prior to reinitiation of study treatment. Additionally, relevant safety laboratory assessments, including both full hematology and full chemistry results within 2 weeks, must be available and verified. The clinical Investigator will determine whether additional evaluation and work-up are required on a case-by-case basis. A discussion with the study team is warranted to determine whether PK/CCI testing is indicated upon restarting treatment.

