7.1.3.3 Continuation of Study Intervention After Local Treatment of Disease Progression

If disease progression is due to brain metastasis, participants may continue study interventions after the local treatment of the brain lesions provided that the above criteria are met in addition to the following:

- Tumor assessment showing disease progression has been performed and was documented according to RECIST 1.1 prior to the procedure.
- Brain metastases have been treated locally and are clinically stable for at least 2 weeks prior to reinitiation of study interventions.

- There are no ongoing neurological symptoms that are related to the brain localization of the disease (sequelae that are a consequence of the treatment of the brain metastases are acceptable).
- Participants must be either off steroids or on a stable or decreasing dose of ≤ 10 mg daily prednisone (or equivalent).
- Benefit-risk assessment to continue study intervention is favorable under consideration of any alternative treatment options as assessed by the Investigator.

In addition, if disease progression is mainly due to a metastatic lesion which in the opinion of the Investigator may be surgically removed, participants may continue study interventions after the local treatment of such a lesion provided that:

- Tumor assessment showing disease progression has been performed and was documented according to RECIST 1.1. prior to the procedure.
- It has been at least 2 weeks and the participant has fully recovered from the surgery.
- Benefit-risk assessment to continue study intervention is favorable under consideration of any alternative treatment options as assessed by the Investigator.

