6.1 Overview of Planned Analyses after discontinuation of NSCLC and BTC trials

The data review outcome from the 3 randomized controlled studies in NSCLC (Non-Small Cell Lung Cancer) and BTC (Biliary Tract Cancer) (MS200647-0005, MS200647-0037, MS200647_0055) appears to indicate, consistently across 2 indications, either poorer observed hazard ratios for PFS and OS in the experimental arms with bintrafusp alfa or low likelihood for bintrafusp alfa to add benefits compared to standard of care.

Based on this, the decision was made to restrict the analyses on this study MS200647-017. The analyses described in Table 2 will not be performed as planned, but one analysis based on the primary analysis cutoff of 15 February 2022 will be performed for an abbreviated CSR (aCSR).

The analyses considered relevant for this purpose are listed below:

- Participant disposition
- Important protocol deviations
- Demographics, medical history and other baseline characteristics (disease history, HPV and PD-L1 test at screening, vital signs at baseline, skin status history)
- Vaccines for COVID 19
- Previous and concomitant medications, procedures, follow-up treatments
- Treatment exposure and compliance
- Efficacy analyses:
 - ORR per RECIST 1.1 as assessed by IRC
 - ORR and DCR per RECIST 1.1 as assessed by IRC
 - Reasons for Non-evaluable BOR based on Confirmed Responses according to RECIST 1.1 as Adjudicated by IRC
 - Percent Change from Baseline in Sum of Diameters according to RECIST 1.1 as Adjudicated by IRC
 - Percent Change in Sum of Diameters between Baseline and Best Post-baseline Assessment according to RECIST 1.1 as Adjudicated by IRC and selected subgroups
 - ORR per RECIST 1.1 as assessed by IRC - Forest plot of odds ratio by subgroups
 - ORR and DCR per RECIST 1.1 as assessed by Investigator

- Concordant and Discordant Objective Response based on confirmed responses according to RECIST 1.1 between IRC and Investigator
- PFS per RECIST 1.1 as assessed by IRC
 - PFS per RECIST 1.1 as assessed by IRC - Kaplan-Meier Curve
 - PFS per RECIST 1.1 as assessed by IRC by histology and PD-L1 - Kaplan-Meier Curve
 - PFS per RECIST 1.1 as assessed by IRC - Forest plot of hazard ratio and free survival rates at 6 and 12 months by subgroups
 - PFS per irRECIST 1.1 as assessed by IRC - Kaplan-Meier Curve
- Duration of response per RECIST 1.1 as assessed by IRC
 - Duration of response per RECIST 1.1 as assessed by IRC - Kaplan-Meier Curve

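### The waterfall and spider plots have no stated cut at subsequent anticancer therapy, so shrinkage from a later treatment can appear as best change on bintrafusp alfa

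*SAP*

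**What the plan says.** SAP 14.1.1, under the details of analyses, sets the rule for both displays: "All sum of diameters will be used, including the ones beyond first PD". For the waterfall it adds that "the best post-baseline sum of diameters will be used even if occurring beyond PD". One filter applies: only valid timepoints are plotted, where "a valid timepoint assessment is defined as a complete assessment of all target lesions reported at baseline", with split and coalesced lesions handled. The spider plot shows each participant's curve "together with the first occurrence of new lesion and the participant off treatment". The waterfall also shows the change at the 8-week assessment, and a version is presented with confirmed BOR per IRC and with baseline subgroups.

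Earlier in the same section, BOR has a cut: "Only tumor assessments performed before the start of any subsequent anti-cancer therapies will be considered in the assessment of best overall response". A scan on the day the new therapy starts counts as before it. PFS Rule 1 (SAP 14.2.4, Table 7) censors at the last tumor assessment before new anticancer therapy, and counts surgery and radiotherapy as such therapy.

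SAP 6.1 keeps both displays for the abbreviated report, the second as "Percent Change in Sum of Diameters between Baseline and Best Post-baseline Assessment according to RECIST 1.1 as Adjudicated by IRC and selected subgroups".

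The protocol also foresees local treatment without stopping the drug. In 7.1.3.3, for a progressing metastasis that can be removed surgically, "participants may continue study interventions after the local treatment of such a lesion provided that" the listed conditions are met. Section 6.5.3 permits palliative radiotherapy. For participants who restart, 7.1.2.1 says: "A rebaseline scan must be performed prior to reinitiation of study treatment".

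**The concern.** Within one section, the response label and the bar height follow different rules. The label ignores scans after a switch of therapy; the bar does not. A participant labelled SD or PD can carry a deep negative bar earned on next-line treatment, and the waterfall has no stated mark for the switch.

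This is easy to misread here. The Phase I study reported a partial response after confirmed progression (Protocol 2.2), and SAP 14.1.1 plans a spider plot that includes delayed responders. Shrinkage on a later therapy would look much the same as a delayed response. What is at stake is the reading of two efficacy figures and their subgroup displays, not an estimate or a decision.

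**Working it through.** The plan states no figure for these plots, so there is nothing to reproduce. The check compares the rules and then works through what they imply.

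**1. Rules side by side**

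| Output | Stops at subsequent anticancer therapy? | Source |
|---|---|---|
| BOR and ORR | Yes, same-day scan included | SAP 14.1.1 |
| PFS, Rule 1 | Yes, by censoring | SAP 14.2.4, Table 7 |
| DOR, and DRR through it | Yes, uses the PFS censoring rules | SAP 14.2.8, 14.2.10 |
| Waterfall, spider | No cut stated | SAP 14.1.1 |

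The valid-timepoint filter tests completeness, not attribution. A complete scan on next-line therapy passes it.

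**2. Direction**

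Let A be the sums up to the switch and B the sums after it. The plotted best value is min(A and B together), which is never larger than min(A). Adding B cannot make a bar shallower.

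**3. When a bar moves**

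Let the sum at the switch be k times the smallest sum on drug. A fractional fall f on the next therapy sets a new minimum only if (1 - f) × k < 1, that is f > 1 - 1/k.

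- Progression by new lesion only, target sum still at its minimum (k = 1): any fall deepens the bar.
- Progression at exactly 20% above the minimum (k = 1.20): f must exceed 1 - 1/1.20 = 16.7%. A 30% fall gives 0.70 × 1.20 = 0.84 of the on-drug minimum.

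**4. Illustration (all values in mm, assumed)**

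Baseline 100, best on drug 90, progression at 125, so k = 125/90 = 1.39.

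- With the BOR cut: (90 - 100)/100 = -10%.
- Next therapy brings the sum to 65: (65 - 100)/100 = -35%. This needs a fall of 60/125 = 48% from progression.
- Next therapy gives only a 30% fall: 0.70 × 125 = 87.5, plotted at -12.5%, barely different from -10%.

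The effect on one bar therefore ranges from nothing to large.

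**5. Local treatment of a target lesion (assumed)**

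Baseline lesions 60 + 40 = 100; sums 104 and then 128 on drug; the second lesion is removed while the first measures 66.

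- Removed lesion scored 0 mm: (66 - 100)/100 = -34%.
- Removed lesion scored not evaluable: the timepoint is not valid and is dropped; the best change stays (104 - 100)/100 = +4%.

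The visible text does not say which scoring applies. SAP 9.8 takes subsequent therapy from the after-discontinuation eCRF pages, so a date cut built on those pages might miss local treatment given while the drug continues.

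**6. Reinitiation**

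Protocol 7.1.2.1 restarts bintrafusp alfa at the same dose and schedule. SAP 9.2 fixes baseline before the first dose, and no visible text measures the plotted change against the rebaseline scan. Sums after reinitiation are still on-drug values against the original baseline.

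**The case against.** The best defence has four parts.

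- **Plotting beyond progression is deliberate.** It fits treatment beyond progression and the interest in delayed response. This stands: sums after progression on bintrafusp alfa should stay. It does not justify sums obtained on another therapy.
- **The reader has warnings.** The spider plot marks off treatment, and points after a switch should normally fall after that mark. A deep waterfall bar beside a BOR of SD or PD is visibly discordant, and both tumor listings give the date of subsequent therapy. This stands in part. It would be wrong to say the reader has no sign at all, but off treatment does not date the new therapy, and discordance does not tell a delayed response from next-line shrinkage.
- **Exposure may be small.** Long-term follow-up is by chart review or telephone, and the Table 7 row on events after new therapy could be filled by deaths alone. Whether the IRC measures scans after a switch cannot be seen, since Protocol 8.1 is redacted, and redacted SAP subsections could hold related rules. This stands and limits any claim about frequency.
- **Little depends on it.** The two displays are among about twenty efficacy outputs kept in SAP 6.1, and no estimate changes. This also stands.

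A reader might infer more than the text supports. Rebaselining does not create false shrinkage, because restart is with the same drug and the baseline is not reset. Resection inflates a bar only under a score of 0 mm that the plan does not state, and the removed lesion may not have been a target lesion. A count of affected bars would need rates of switching and rescanning that the documents do not give.

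**Conclusion.** The point holds as a gap in two descriptive figures. As written, the plotted sums have no cut at subsequent anticancer therapy, the waterfall takes the minimum, and any resulting error deepens bars. Shrinkage from a later therapy can therefore be shown as best change on bintrafusp alfa and can contradict the BOR presented with it.

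For one participant the effect can be nil, small (-12.5% for -10%) or large (-35% for -10%) on the assumed values above. The number of participants affected cannot be determined from the documents. The conclusion assumes that some target-lesion measurements exist after a switch and that no redacted passage already sets a cut.

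It would be wrong to infer that the primary result is biased. ORR, DOR, DRR and Rule 1 PFS do not use these sums and have their own cuts. This is a cheap improvement to figures kept for the abbreviated report, not a threat to its conclusions.

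**What to change.** In SAP 14.1.1, and in the Investigator repeat in 14.2.1 if those plots are produced:

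- Limit waterfall and spider sums to assessments on or before the start of any subsequent anticancer therapy, using the BOR cut and its same-day rule.
- Keep sums after progression obtained on bintrafusp alfa, including after reinitiation, unless another anticancer therapy came in between. No exclusion tied to the rebaseline scan is needed.
- Treat a target lesion removed or irradiated after the start of study treatment as not evaluable for these plots, so that the valid-timepoint filter drops that sum. Limiting this to treatment on study preserves the planned spider plot of previously irradiated target lesions.

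The cost is a sentence or two in the SAP and a date filter on a date the tumor listings already carry; local treatment given while the drug continues must be identified from the procedure records. Some late points, including on-drug sums after local treatment of a target lesion, would no longer be plotted. They remain in the tumor listings.
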